8.1.7 Pooling of Sites

Data collected from all sites will be pooled together for the analysis.

8.2 Subject Disposition and Withdraws

The number of patients who enter screening will be summarized, and the percentage of these patients who fail to meet entry criteria will be reported for total subjects. Screen failures will be summarized in total and by each reason for screen failure.

Subject disposition will be summarized for patients' **completion status** of study treatment, status of outcome/discharge, and corresponding discontinuation reasons in tables for each treatment group and then total subjects. The data listing for subject discontinuation will be generated.

8.3 Demographic and Baseline Characteristics

Patient demographic and baseline characteristics will be summarized by mean, SD, median, minimum, and maximum for continuous variables; interquartile ranges for nonparametric data, and by counts and percentages for categorical variables. Summaries will be provided separately for each treatment group and then total subjects. The following subject demographic and baseline characteristic are summarized. The demographic variables consist of age, age category (18-39, 40-64, 65+), sex, ethnicity, and race. Baseline characteristics include height, weight, body mass index (BMI), time from symptom onset to randomization in days, the number of SIRS criteria met at Screening: two versus greater than two, number of patients at high risk for organ failure [defined by the presence of both an elevated hematocrit (HCT ≥44% for men or ≥40% for women) and hypoxemia (imputed PaO₂/FiO₂ ≤360)], number of patients with baseline hematocrit value and category (<44%, >=44% for males; <40%, >=40% for females), the number of patients with abdominal guarding or rebound tenderness, and the number of patients

Protocol CM4620-203 CONFIDENTIAL Page 13 of 31

with CECT at Screening with peripancreatic fluid or pleural effusion by central reading. The Modified Intent to Treat (MITT) Analysis Set will be used for the summaries.

Other baseline variables such as relevant medical history or other medically relevant criteria, such as the cause of acute pancreatitis, will also be included in the baseline tables.

8.4 Concomitant Medications

CalciMedica Inc.

Concomitant medication is defined as any medication, other than study medication, which is taken on or after the start day of treatment. The concomitant medication data will be coded using World Health Organization Drug Dictionary (B3 WHO Drug DDE – Sep 2019 or the later version). The number and percentage of subjects taking selected concomitant medications will be summarized overall and by Anatomic Therapeutic Chemical (ATC) Classification level 2 terms, preferred drug names and treatment groups. A separate listing for selected concomitant medications will also be provided.

8.5 Study Medication Exposure

The number of treatment doses, delayed doses, reduced doses, and interrupted doses per patient of double-blind study medication will be summarized in the table for the MITT population. The percentage of delayed doses, reduced doses, and interrupted doses per patient and per total number doses will be summarized.

8.6 Primary Endpoint Analysis

8.6.1 Generalized Multiple Comparisons and Modelling (gMCP-Mod)

The primary objective of this study is to demonstrate a dose-response effect of Auxora compared to placebo of the primary endpoint time to solid food tolerance through Day 30. To demonstrate the dose-response relationship between treatment with Auxora compared to placebo for the primary endpoint, the primary analysis will be based on a generalized Multiple Comparisons and Modeling (gMCP-Mod) analysis [Bretz et al., 2005; Pinheiro et al., 2014]. This analysis tests for a dose-response relationship, allowing for uncertainty in the dose-response relationship through inclusion of contrasts from multiple pre-specified candidate models assessing dose-response.

This is accomplished by decoupling the dose-response model from the expected response through the use of an ANOVA-style parameterization of the dose-response parameter. For the time-to-event endpoint used in this study, a stratified Cox regression of the time to solid food tolerance at each dose level will be used, stratified by the CRF recorded sex (male or female) and then by risk for organ failure based on CRF data in the sex subgroups (higher or lower). After this first step, the mean estimates of log hazard ratio from the Cox regression model and the corresponding covariance matrix, both of which are on the log scale, will then be used during the rest of the gMCP-Mod procedure. Point estimates from the selected models will be displayed on the ratio scale in all statistical outputs.

The gMCP-Mod (Pinheiro et al., 2014) will be employed in a three-step approach in the manner described below:

Protocol CM4620-203 CONFIDENTIAL Page 14 of 31

• Step 1: Conventional Step – Hazard Ratio Between Each Dose Versus Placebo

The data are analyzed using stratified Cox regression to obtain treatment effects and corresponding variance covariance matrix. The Cox regression will be stratified by sex (male or female) and the risk for organ failure (higher or lower).

The estimated treatment hazard ratio and the associated 95% confidence intervals will be presented for the treatment contrast of each dose of Auxora versus placebo

• Step 2: Proof-of-concept Step – Candidate Models and Multiple Testing Procedure

The null hypothesis of flat dose-response relationship as compared to placebo for the primary efficacy endpoint will be tested at a significance level of one-sided 15% against the alternative hypothesis of a non-constant dose-response curve using a multiple contrast test as described in the gMCP-Mod methodology (Pinheiro et al., 2014). The contrast test statistic is a linear combination of the optimal contrast coefficients corresponding to the candidate dose-response curve with the hazard ratio at each individual dose obtained from Step 1 (conventional step).

The contrast coefficients are chosen to maximize the power to detect pre-specified candidate models. There are two candidate models that will be considered for the primary analysis with the optimal contrasts shown in following table. These optimal contrasts will be updated using the expected model means from the candidate set of the two models and the estimated variance-covariance matrix from the collected data. The updated contrast coefficients will be described in the final CSR.

The optimal contrast based on Candidate models for Auxora dose for log(Hazard Ratio):

Model	Contrast Coefficients for Dose					
Dose	0.5 mg/kg	1.0 mg/kg	2.0 mg/kg			
Emax	0.508	0.588	0.629			
sigEmax	-0.611	0.488	0.623			

Note: Candidate model of Emax model is based on the assumption of parameter of ED50=0.026 mg/kg. Candidate model of sigEmax mode is based on the assumption of parameters of ED50=0.707 mg/kg and h=6.34.

The proof of concept (PoC) is established if at least one dose-response model is statistically significant, thereby rejecting the null hypothesis of a flat dose-response curve and indicating a benefit of Auxora over placebo.

The global test decision is based on the maximum of the contrast test statistics. A critical value q controlling the type I error rate can be derived from the fact that the contrast test statistics approximately follow a multivariate normal distribution and that their maximum

Protocol CM4620-203 CONFIDENTIAL Page 15 of 31

follows the distribution of the maximum of a multivariate normal distribution. If the maximum contrast test statistic exceeds the critical value q, the overall null hypothesis of a flat dose-response curve is rejected, and one proceeds to characterize the dose-response efficacy relationship.

For each candidate dose-response curve, the test statistics and corresponding adjusted p-values will be presented.

Once proof of concept has been established, then subsequently, it will be tested whether at least one dose of Auxora achieves time to solid food tolerance superior to placebo (i.e., the maximum anticipated effect of Auxora for achieving the primary endpoint, based on the best fitting monotonic dose-response model).

• Step 3: Dose-finding Step – Dose-Response Model Fitting

Once the significance of a dose-response signal is established, the dose-response profile and the target dose can be estimated using the best-fitting dose-response model. All significant dose-response models will be re-fitted to the data without any parameter assumptions to generate a set of new estimates of the model parameters from the data. The final dose-response model will be obtained via the model with the smallest Akaike Information Criterion (AIC) (the smaller the AIC value the better the model fit). Estimates for the dose groups will be calculated and will be based on the final dose-response model.

The dose-response curve estimate with the model-based two-sided 95% confidence interval will be presented graphically. In addition, the plot will include the mean responses from the Cox Regression and the associated 95% confidence intervals for each of the studied dose groups.

The target dose(s) suggested by gMCP-Mod based on time to solid food tolerance serves as an important consideration in dose selection. However, the final dose selection will be determined based on the following:

- Efficacy of doses based on the totality of efficacy data
- Safety endpoints including AEs, and SAEs

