CM4620-IE Dose and Route of Administration:	Patients randomized to receive Auxora (also known as CM4620 (zegocractin) Intravenous Emulsion) will receive one of three dose levels, 2.0 mg/kg (1.25 mL/kg), 1.0 mg/kg (0.625 mL/kg), and 0.5 mg/kg (0.3125 mL/kg), every 24 hours (±1 hour) for three consecutive days for a total of three infusions (Section 5.3). Auxora will be administered intravenously as a continuous infusion over 4 hours via a bag and tubing compatible with lipid emulsions and using a 1.2-micron filter.
Placebo Dose and Route of Administration	Placebo will consist of the emulsion without any active pharmaceutical ingredient CM4620. Patients randomized to receive Placebo will receive one of three dose volumes, 1.25 mL/kg, 0.625 mL/kg, and 0.3125 mL/kg, every 24 hours (±1 hour) for three consecutive days for a total of three infusions (Section 5.3). Placebo will be administered intravenously as a continuous infusion over 4 hours via a bag and tubing compatible with lipid emulsions and using a 1.2-micron filter.
Objectives:	 Primary: To assess the dose response and efficacy of three different dose levels of Auxora in patients with AP and accompanying SIRS; To assess the time to medically indicated discharge in patients who are responders to early tolerance of solid food intake versus non-responders. Secondary: To assess the safety and tolerability of varying doses of Auxora in patients with AP and accompanying SIRS.

Inclusion Criteria:

All of the following must be met for a patient to be randomized into the study:

- 1. The diagnosis of AP has been established by the presence of abdominal pain consistent with AP together with at least 1 of the following 2 criteria:
 - a. Serum lipase > 3 times the upper limit of normal (ULN);
 - b. Characteristic findings of AP on abdominal imaging;
- 2. The diagnosis of SIRS has been established by the presence of at least two of the following four criteria:
 - a. Temperature $< 36^{\circ}$ C or $> 38^{\circ}$ C;
 - b. Heart rate > 90 beats/minute;
 - c. Respiratory rate >20 breaths/minute or arterial carbon dioxide tension (PaCO₂) <32 mmHg;
 - d. White blood cell count (WBC) >12,000 mm³, or <4,000 mm³, or > 10% immature (band) forms;
- 3. At least one of the following criteria is also present:
 - a. A peripancreatic fluid collection or a pleural effusion on a contrastenhanced computed tomography (CECT) performed in the 24 hours before Consent or after Consent and before Randomization;

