Subjects in the second group of CM4620-102 were randomized to receive a single dose of active treatment, 1.0 mg/kg, versus placebo for seven consecutive days. Eight healthy subjects were enrolled in the second group, with six receiving active treatment and two receiving placebo for seven consecutive days. There were no SAEs and no AEs classified as moderate or severe in intensity. There were three AEs that were all classified as mild in intensity. In each case, no action was taken with respect to study treatment because of the AEs. No laboratory abnormalities were observed that were considered clinically significant.

There were vehicle-related increases in serum triglyceride noted in some subjects in both groups with levels returning to baseline within 24 hours. Cholesterol levels accumulated in some subjects in both groups with daily dosing, but the increases were not considered clinically significant and were related to the vehicle. Thus, the largest rise in cholesterol levels was in the subject who received placebo at the maximum dose volume of emulsion. The rise in cholesterol is believed to be due to the release of tissue cholesterol induced by the lecithin in the emulsion (Byers 1962), was noted in the pre-clinical studies in monkeys, and was reversible with cessation of dosing. There was no evidence of any sustained treatment related increase in systolic or diastolic blood pressure. In addition, cardiac function, monitored by continuous electrocardiographic recording and serial biomarker testing, showed no evidence of any sustained treatment related effect on heart rate, QTcF or B-type natriuretic peptide levels.

Non-compartmental PK analysis of Group 1 in CM4620-102 (0.5 mg/kg) indicates that zegocractin accumulated in plasma, with a 2.6-fold increase in systemic exposure (AUC_{24h}) on Day 7 compared to Day 1 of dosing, consistent with modeling simulations. C_{max} accumulated 1.6-fold (geometric mean of 363 ng/mL on Day 7). The geometric mean of the AUC_{24h} on Day 7

a one placebo patient received maximum dose volume of 1.3 mL/kg

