Balthazar scores, indicative of increased pancreatic inflammation, whereas 2/8 patients (25%) in the low dose regimen group showed an increase in their scores. These data suggest that doses or systemic exposures associated with the high dose regimen provide the greatest opportunity for efficacy with acceptable tolerability. Since 75% of patients receiving the low dose regimen showed no worsening in their Balthazar scores, these doses may also be efficacious, albeit slightly less than those in the high dose regimen. The specific dose levels of 2.0 and 1.0 mg/kg were selected for the current study to closely match the Day 1 doses of the high and low dose regimens in the Phase 2a study, respectively. Doses notably higher than 2.0 mg/kg (1.25 mL/kg) were not selected as they carry increased risk of intolerance to either zegocractin or lipid load from the emulsion vehicle. The third dose level of 0.5 mg/kg was chosen to help define a minimum efficacious dose level. Adjustment of the zegocractin dose for body weight is based on covariate analysis from a popPK model that was developed from previous Phase 1 and Phase 2a studies. Dose adjustment is not being made for gender or race based on the absence of substantial covariate effects on the popPK model. The 3 dose levels selected are expected to achieve significant separation of plasma exposures on Day 1 (C_{max} and AUC₀₋₂₄) based on popPK modeling. Furthermore, 3 dose levels are considered adequate for dose-ranging studies, as described in International Conference on Harmonization (ICH) guidance E4.

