7 STUDY DRUG MATERIALS AND MANAGEMENT

7.1 Auxora Product Description

Auxora is to be administered as an IV infusion and is supplied as a translucent, white to yellowish colored, sterile, non-pyrogenic emulsion containing 1.6 mg/mL of the active pharmaceutical ingredient zegocractin. Auxora is supplied as an 80 mL fill in a 100 mL, single-use glass vial. The drug product is formulated as an emulsion due to the low solubility of zegocractin in aqueous solution. Auxora contains egg phospholipids, medium chain triglycerides, glycerin, edetate disodium salt dehydrate (EDTA), sodium hydroxide (as needed to adjust pH), and sterile water for injection (Table 4).

Table 4. Auxora Product Information

Product Name:	Auxora		
Dosage Form:	Injectable Emulsion (Liquid)		
Concentration	1.6 mg/mL		
Route of Administration	IV		
Physical Description	Translucent, non-separated, white to yellowish emulsion		
Inactive Ingredients	Sterile Water for Injection USP, Egg Phospholipid NF (80% Phosphatidylcholine), Medium Chain Triglycerides NF, Glycerin USP, and Edetate Disodium Salt Dihydrate (EDTA) USP. Sodium Hydroxide and Hydrochloric Acid may be added to adjust the pH.		

IV = intravenous

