randomized to Group 2 will receive 1.0 mg/kg (0.625 mL/kg) of Auxora intravenously every 24 hours (±1 hour) for a total of three doses. Patients randomized to Group 3 will receive 0.5 mg/kg (0.3125 mL/kg) of Auxora intravenously every 24 hours (±1 hour) for a total of three doses. Patients randomized to Group 4 will receive emulsion without any active pharmaceutical ingredient (placebo). Patients in Group 4 will receive one of three randomly assigned dose volumes, 1.25 mL/kg, 0.625 mL/kg, or 0.3125 mL/kg, which will be administered intravenously every 24 hours (±1 hour) for a total of three doses. The dosing will be based on actual body weight obtained at the time of hospitalization or screening for the study. As described in the pharmacy manual, the upper limit of the volume of Auxora and volume of placebo that will be administered will be 156.25 mL. The sponsor, investigators and patients will be blinded to the assigned group. In the event of a medical emergency, investigators will be able to receive the treatment assignment if required to provide optimal care of the patient.

For all 4 groups, a study physician or appropriately trained delegate will perform assessments at screening, at the baseline assessment, immediately prior to the SFISD, and then every 24 hours until 240 hours after the SFISD, or until discharge if earlier. If patients remain hospitalized at Day 12, assessments will then be performed every 48 hours starting on Day 12 until Day 28, or until discharge if earlier. Patients discharged from the hospital before Day 25 will return at Day 30 (+5 days) to perform the Day 30 assessments. If patients are discharged on Days 25-29, the Day 30 assessments may be performed prior to discharge.

Patients will receive another CECT of the abdomen/pancreas at the Day 30 (±5 days) visit. All CECTs performed as standard of care after randomization and before the Day 30 CECT will also be captured. A blinded central reader will read the Screening, Day 30, and any standard of care CECTs obtained between randomization and 30 days.

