4. SAMPLE SIZE

A sample size of 216 patients will be randomized into four groups on a 1:1:1:1 basis, resulting in 54 patients randomized into each group. This sample size will provide 86% power for testing the difference in two populations having a median length of time of 72 and 144 hours, respectively, to tolerating solid food. This sample size will provide 80% power with a two-sided alpha of 0.05 to detect a 45% response rate for tolerating solid food in an Auxora dose group versus a 20% response rate in the placebo group in the 72 hours after completion of the first study drug infusion.

Protocol CM4620-203 CONFIDENTIAL Page 9 of 31

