8.10.3 Laboratory Analyses

Local laboratory test results will be used in the summary. CBC with differential, platelets, serum chemistries, and serum procalcitonin will be summarized.

Laboratory values by visit will be summarized as boxplots. The lower and upper reference range values for lab tests will be used to grade the lab results to low, normal, and high categories. Shift tables will display:

- Shift from baseline category to the worst category
- Shift from baseline category to the last category

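### Placebo volume is randomised to match the three Auxora doses but is never used in the analysis, so a vehicle-driven lipid rise could look like a drug effect at 2.0 mg/kg

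*SAP*

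**What the plan says.** Protocol 7.1 describes a single product strength, an "emulsion containing 1.6 mg/mL of the active pharmaceutical ingredient zegocractin". The protocol synopsis gives the three doses with their volumes: "2.0 mg/kg (1.25 mL/kg), 1.0 mg/kg (0.625 mL/kg), and 0.5 mg/kg (0.3125 mL/kg"). Placebo is the same emulsion without zegocractin (Protocol 7.2). SAP 3.1 adds: "Patients in Group 4 will receive one of three randomly assigned dose volumes, 1.25 mL/kg, 0.625 mL/kg, or 0.3125 mL/kg". Each group has 54 patients (SAP 4). Neither document states how the placebo patients are divided among the volumes.

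The SAP then treats placebo as a single group:

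- **Primary analysis (8.6.1):** the Cox and gMCP-Mod results are "presented for the treatment contrast of each dose of Auxora versus placebo".
- **Other efficacy analyses:** the log-rank tests (8.6.5), the stratified proportion tests (8.7), the Finkelstein-Schoenfeld and win ratio analyses (8.9) and the subgroups (8.12) all use one placebo group. Some sensitivity analyses merge it with the 0.5 mg/kg arm, again undivided.
- **Safety:** the adverse event tables have one placebo column (8.10.1.1). For laboratory data, "CBC with differential, platelets, serum chemistries, and serum procalcitonin will be summarized" (8.10.3), and tables are laid out by treatment group (11).

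Placebo volume does not appear as a covariate, stratum, sensitivity analysis or table column. PK is analysed separately (8.11), in patients who received active drug (Protocol 10.4.2).

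The protocol attributes triglyceride and cholesterol rises in Phase 1 to the vehicle (1.5.1). In the multiple-dose study cholesterol accumulated with daily dosing, and "the largest rise in cholesterol levels was in the subject who received placebo at the maximum dose volume of emulsion". Total cholesterol and triglycerides are among the serum chemistries collected (Protocol 8.12.7).

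**The concern.** At a fixed concentration, dose and emulsion volume are perfectly collinear in the active arms, so those arms cannot separate drug from vehicle. Only Group 4 can, because its volume is randomised independently of drug. The design provides the information and the analysis plan leaves it unused.

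The practical risk is in the lipid data. A rise caused by the emulsion alone would be larger at 2.0 mg/kg than in pooled placebo and could be read as a drug effect. SAP 8.6.1 (Step 3) makes safety one of the two stated bases for the final dose choice. Volume also rises in the same order as dose, so a vehicle effect on eating, if there were one, would enter the dose-response test.

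**Working it through.** **Plan's own figures.** The 80% power (Protocol 10.2: 54 per group, 45% versus 20%, two-sided 0.05, chi-squared) reproduces:

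- Pooled rate 0.325; null SE = √(2 × 0.325 × 0.675 / 54) = 0.0901.
- Alternative SE = √((0.2475 + 0.16) / 54) = 0.0869.
- z = (0.25 − 1.96 × 0.0901) / 0.0869 = 0.844, so power is 80.1%.

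This is for one dose against all 54 placebo patients.

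**Volume imbalance.** Assume 1:1:1, that is 18 placebo patients per volume.

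- Mean placebo volume = (0.3125 + 0.625 + 1.25) / 3 = 0.729 mL/kg, SD 0.390.
- Gaps to pooled placebo: 0.5 mg/kg, −0.417; 1.0 mg/kg, −0.104; 2.0 mg/kg, +0.521 mL/kg. They sum to zero.
- Lipid load at 2.0 mg/kg relative to pooled placebo = 1.25 / 0.729 = 1.71.
- Range over other splits: with half of placebo on the lowest volume and a quarter on each of the others, the mean is 0.625 and the ratio 2.0. With half on the highest and a quarter on each of the others, the mean is 0.859 and the ratio 1.45.

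**Efficacy illustration.** Assume no drug effect and a log-linear vehicle effect β per mL/kg. Each dose's log hazard ratio then shifts by about β × gap. At 2.0 mg/kg the shift is ln(1.25) × 0.521 = 0.12 for an assumed vehicle hazard ratio of 1.25, and ln(1.5) × 0.521 = 0.21 for 1.5. Applying the SAP's printed contrasts to the gaps gives a sensitivity per unit β of 0.055 for Emax and 0.528 for sigEmax.

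Take the covariance of the three log hazard ratios as I/(events per active arm) + J/(placebo events), where I is the identity matrix and J the matrix of ones. With 46 and 31 events this reproduces the printed contrasts to within 0.002. It fixes only the ratio of the counts: 23/15.5 and 54/36.4 give the same contrasts. The contrast correlation is 0.605 and the one-sided 15% critical value 1.324. Probability of passing:

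| Events (active/placebo) | Vehicle HR 1.25 | Vehicle HR 1.5 |
|---|---|---|
| 23 / 15.5 | 24% | 35% |
| 46 / 31 | 29% | 48% |
| 54 / 36.4 | 31% | 52% |

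The Emax contrast alone passes about 10% of the time in every cell, against 9% under the null. In the other direction, an assumed vehicle hazard ratio of 0.67 lowers the pass rate to about 8% to 9%.

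**What the placebo arm can tell.** SE of the vehicle slope = 1 / (√events × 0.390), which is 0.46 with 31 placebo events and 0.36 with 50. The correction at 2.0 mg/kg has SE 0.521 × slope SE, or 0.24 and 0.19. Power to detect the slope is 8% to 9% at a hazard ratio of 1.25 and 14% to 20% at 1.5.

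**Cost of volume-matched inference.** For 54 active against 18 matched placebo patients, the pooled rate is 0.3875, the null SE 0.1326 and the alternative SE 0.1161. Then z = (0.25 − 1.96 × 0.1326) / 0.1161 = −0.085, so power is 46.6% instead of 80.1%.

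**The case against.** A reader might infer that vehicle effects are contaminating the efficacy dose response. The documents do not support that. They report vehicle effects on triglycerides and cholesterol only, none on tolerance of solid food. Where Protocol 1.6 says "they carry increased risk of intolerance to either zegocractin or lipid load from the emulsion vehicle", it is speaking of doses notably above 2.0 mg/kg, which are not studied. The vehicle hazard ratios, the 1:1:1 split and the event counts used above are assumptions, and under 1:1:1 all Auxora against all placebo is balanced on volume. A volume-adjusted model would not settle the question either: its correction SE (0.19 to 0.24) is about as large as the bias it would remove (0.12 to 0.21). All of this stands.

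A second tempting reading is that pooling placebo is itself an error. It is not. The estimand (SAP 8.6.2) defines each treatment as a dose together with its volume, and volume-matched comparisons would lose much of the power.

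On safety, the analysis is descriptive, there is no dedicated lipid table, and the protocol already ascribes the cholesterol rise to the vehicle and does not regard it as clinically significant. Triglycerides returned to baseline within 24 hours in Phase 1, and the 24- and 48-hour samples precede the next infusion (although blood from the previous 12 hours is allowed), so a large triglyceride artefact is doubtful. This weakens the triglyceride case. It does not remove the cholesterol case: the Phase 1 attribution rests partly on one maximum-volume placebo subject, and this trial could check it in about 18.

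**Conclusion.** The point holds as an omission: a randomised factor that could separate drug from vehicle is left out of every analysis and table. Its firm consequence is for lipid interpretation, mainly cholesterol. The 2.0 mg/kg arm receives 1.7 times the mean placebo lipid load under a 1:1:1 split, and 1.45 to 2.0 times under the other splits tried.

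For efficacy, the conclusion is limited to structural possibility. The 24% to 52% pass rates show how the sigEmax contrast would respond if a vehicle effect of the assumed size existed. They are not evidence that one does. The plan's 80% power figure is not in dispute.

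**What to change.** 1. Keep pooled placebo for the primary analysis and for all inference.
2. In SAP 8.10.3, for total cholesterol and triglycerides, show placebo split by randomised volume, each beside the Auxora dose with the same volume. Do the same, descriptively, in the adverse event overview (8.10.1.2).
3. State the planned allocation of placebo patients to the three volumes.
4. In SAP 8.7.8, 8.9 and 8.12, name the active groups by mg/kg; the mL/kg labels used there also describe placebo patients.
5. Optionally, add one exploratory stratified Cox model with three dose indicators plus randomised volume, where the placebo arm identifies the volume slope. Report it with its confidence interval and say that it assumes a log-linear vehicle effect common to drug and placebo, and is too imprecise to confirm or exclude modest vehicle effects.

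The cost is SAP wording and a few table columns. No new data are needed. The drawback is small cells, about 18 patients per volume if the split is 1:1:1, so the columns should be read descriptively.
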